5.10. Interim Analyses

[figure not shown]
The study originally planned interim analyses at approximately 25%, 50% and 75% of participants completing the trial. Due to rapid enrollment, only a single interim analysis was conducted, at the time when enrollment had completed (and ~50% of the patients had completed the trial). This interim analysis was not used to stop the trial early for efficacy or futility, as enrollment had already completed, and occurred at a scheduled safety review by the independent

DMC. This interim was for the purpose of ensuring safety and included efficacy data to assess the risk/benefit.

After the last patient has completed their Day 10 assessment, but prior to final data base lock, an interim analysis will be conducted for the purpose of BLADE to begin Phase 3 planning. Blade plans to amend the current protocol to include a second part that would be a Phase 3 trial. As this is a COVID-19 study and there is an immediate public need for effective therapies, BLADE feels amending the protocol to adopt this second Phase 3 part of the study will significantly reduce the start-up time required to initiate the independent phase 3 (part 2 of the study) study by 4-6 months. This approach was communicated to FDA on 11-September 2020, and the sponsor did not receive any objections to this approach. The Phase 3 portion will be analyzed separately from the Phase 2 portion.

The original interim analysis plans for the Phase 2 portion of the study were as follows. An interim analysis is planned when approximately 25%, 50% and 75% of participants have completed the study for the purpose of early stopping for efficacy or futility. Based on the enrollment rates, one or more of these planned interim analyses may occur earlier in time or may not occur at all.

The Lan-DeMets spending function analog of the O'Brien-Fleming boundaries will be used to monitor each of the primary endpoints as a guide for the DMC for an overall one-sided type-I error rate of 2.5%, for each endpoint. At the time of the planned interim analyses (when approximately 25%, 50% and 75% of participants have completed the study), the amount of information (i.e., information rate) for each primary endpoint will be different, and therefore each endpoint will have a different critical value to determine if the study should be stopped early for efficacy. For the primary endpoint of change from baseline in SpO₂/FiO₂ ratio the amount of information is based on the number of participants (total planned =120), and the interim analyses will occur when approximately, 30, 60, and 90 participants (information rate = .25, .5 and .75) complete the study. For the primary endpoint of time to clinical improvement the amount of information is based on the observed number of events (total planned =75) and the information rate at the time of the interim analyses will depend on the observed number of events at that time (example if there are only 15 events observed at the first planned interim, the information rate at this time point will be $15/75=0.20$). The following plot provides the critical value boundaries based on the O'Brien-Fleming Lan-DeMets spending function.

Conditional power will be used as an additional guide to the DMC to assess futility. Conditional power allows computation of the probability of obtaining a statistically significant result by the end of the study given the data accumulated thus far. If the conditional power is less than 20% based on the observed effect size, for both primary endpoints, consideration will be given to stopping the study.

The conditional power for each primary endpoint will be calculated as,

$$CP_{\hat{\delta}_1}(z_1, \tilde{n}_2) = 1 - \Phi \left(\frac{z_\alpha \sqrt{n_2} - z_1 \sqrt{n_1}}{\sqrt{\tilde{n}_2}} - \frac{z_1 \sqrt{\tilde{n}_2}}{\sqrt{n_1}} \right)$$

where z_1 is the observed Wald test statistic at the interim, n_2 -tilde is the planned sample size for stage 2, n_1 is the sample size for stage 1, and n_2 is the cumulative planned sample size (i.e., $n_2 = n_1 + n_2$ -tilde) and z_α is the value from the inverse normal distribution with $\alpha = 2.5\%$.

At the interim analysis when approximately 50% of the participants have completed the study, a sample size re-estimation step will occur using the promising zone approach (Mehta and Pocock, 2011) and method of Chen, DeMets and Lan, based on the observed effect size at this interim analysis. The promising zone is defined as a conditional power of between 50% and 80%. If the conditional power falls into this region the sample size may be increased to raise the conditional power to 80%.

CONFIDENTIAL

Statistical Analysis Plan [Version 3.0]

The study will not stop enrolment awaiting these DMC reviews, though the DMC may recommend temporary or permanent cessation of enrolment based on their safety reviews.

A separate unblinded statistical team will prepare the above information for the DMC to review and make recommendations to the Sponsor. The following efficacy endpoints will be summarized at each interim analysis using the FAS:

Objectives	Endpoints
Primary	

 To evaluate clinical benefit of BLD-2660 in hospitalized adults with recently diagnosed SARS-CoV-2 infection 	
 Time to recovery as defined by no longer requiring oxygen support or hospital discharge, whichever occurs first

 To evaluate improvement in oxygenation in hospitalized adults with COVID-19 treated with BLD-2660 	
 Change from baseline to Day 10 or hospital discharge, if sooner, in the ratio of peripheral hemoglobin oxygen saturation to fraction of inspired oxygen (SpO₂/FiO₂)
Secondary	

 	

 Additional efficacy outcomes 	
 Time to hospital discharge readiness
Exploratory	

 Other efficacy outcomes 	
 Proportion of participants who require mechanical ventilation after study entry

6. References

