1.2. Study Design

This is a Phase 2 randomized, double-blind, placebo-controlled multicenter study designed to evaluate BLD-2660 as add-on to standard of care (SOC) therapy in hospitalized participants with recently diagnosed COVID-19 compared to SOC treatment.

The study will include a Screening period, a Treatment period, and a Follow-up period.

After signing informed consent form (ICF), potential candidates who are hospitalized for confirmed infection with SARS-CoV-2 will undergo additional screening procedures.

On Day 1, eligible participants will be randomized in 2:1 ratio to one of 2 treatment groups, active or control, as shown in Table 1. Randomization will be stratified by remdesivir at study entry. All participants will receive study drug in combination with SOC over 10 days (through Day 10/end of treatment) or until hospital discharge, if sooner. Participants will be followed for at least 18 days after the last dose of study drug on Days 14, 21 and 28. Participants will be contacted 60 days post-study to collect information on mortality and forced vital capacity (FVC).

CONFIDENTIAL

Statistical Analysis Plan [Version 3.0]

Table 1: Treatment Groups

Treatment Group	Dose Level, Schedule and Route of administration	Number of participants
Active	BLD-2660 900 mg twice per day (BID), oral + SOC	80
Control	Matching placebo, BID, oral + SOC	40

For each participant, the study duration for each study period is expected to last as follows:

Study Period	Duration
Screening period	Up to 3 days
Treatment period	10 days
Treatment Follow-up period	18 days
Post study follow-up period	32 days

Interim analyses are planned when approximately 25%, 50% and 75% of participants have completed the study for the purpose of reviewing safety data and for the purpose of early stopping for efficacy or futility. At the 50% interim analyses, the sample size may be increased.

The final analysis will occur once the last participant enrolled completes the end of study follow-up visit. Data from the post study follow-up visit regarding FVC will be included in the final databased after the final analysis has been completed.

2. Statistical Hypotheses

Two primary statistical hypotheses will be tested. The study will be declared a success if either of the hypotheses are statistically significant. As this is a phase 2 study, no adjustment for multiplicity will be made for having two co-primary hypotheses.

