The primary efficacy endpoint of change from baseline to Day 10 or hospital discharge if sooner, in the ratio of hemoglobin oxygen saturation to inspired oxygen fraction (SpO₂/FiO₂) will be analyzed using a mixed model for repeated measures (MMRM). The Kenward-Roger method will be used to calculate the denominator degrees of freedom for the test of fixed effects and adjusted standard errors. The model will contain treatment, time and the treatment by time interaction as fixed effects and baseline score, age (years), corticosteroid use (yes vs no) and remdesivir strata as covariates. If age and/or corticosteroid use are not significant at the 5% level, they will be removed from the model. As the follow-up visit schedule for each participant will be variable, the following timepoints will be used; Day 1, Day 2, Day 3, Day 4, Day 5 and Day 10/Discharge. Additional time points (e.g., Days 6-9) may be included if most participants are not discharged prior to Day 10. An unstructured covariance matrix will be assumed to model the within-participant errors. This variance-covariance matrix will be estimated across treatment groups. However, if there is a convergence problem with the unstructured covariance matrix, then alternative covariance structures will be examined (heterogeneous Toeplitz structure, Compound Symmetry) and the one with the best fit as determined by the Akaike information criteria (AIC) (i.e., smallest AIC value) will be used. The least squares means (LS-means) for each treatment, LS-means treatment difference and corresponding confidence interval (CI) for the LS-means difference and p-value for the treatment difference, will be reported at the Day10/Discharge timepoint.

The primary analysis will be conducted using the FAS.

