5.5.3. Sensitivity Analysis

Time to Clinical Improvement

The following sensitivity analyses will be conducted:

- 1) The primary analysis will be repeated for the PP analysis set.

Change from baseline to Day 10 or hospital discharge if sooner, in the ratio of hemoglobin oxygen saturation to inspired oxygen fraction (SpO₂/FiO₂)

The following sensitivity analyses will be conducted:

- 1) The primary analysis will be repeated for the MITT analysis set.
- 2) The primary analysis will be repeated for the PP analysis set.

Depending on the amount of missing data, additional sensitivity analyses may be needed. If these are needed, they will be documented in the CSR.

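### The sponsor's interim after the last Day 10 visit is planned before database lock, without saying who is unblinded or that the primary models are fixed first

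*SAP*

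**What the plan says.** SAP section 5.10 describes two looks. The first, already done when enrolment had closed and roughly half the patients had completed, was a safety review by the data monitoring committee. The second is new, is triggered by the last patient's Day 10 visit, and serves the sponsor: "but prior to final data base lock, an interim analysis will be conducted for the purpose of BLADE to begin Phase 3 planning". SAP section 1.2 places the final analysis later: "The final analysis will occur once the last participant enrolled completes the end of study follow-up visit", which is Day 28.

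Section 5.10 then restates the original interim plan. That part ends with a list introduced by "The following efficacy endpoints will be summarized at each interim analysis using the FAS", and the list includes both primary endpoints. It also contains the only firewall: "A separate unblinded statistical team will prepare the above information for the DMC to review". Protocol section 9.5 has the same arrangement and no sponsor look.

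Several parts of the primary analyses are not settled:

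- **Cox model (SAP 5.5.2).** Treatment, remdesivir stratum and age are fixed. Country, chloroquine or hydroxychloroquine, HIV antivirals, corticosteroids and azithromycin are optional, chosen stepwise at p < 0.05.
- **MMRM (SAP 5.5.2).** Age and corticosteroid use are dropped if not significant at 5%. On time points: "Additional time points (e.g., Days 6-9) may be included if most participants are not discharged prior to Day 10".
- **Sensitivity analyses (SAP 5.5.3).** "Depending on the amount of missing data, additional sensitivity analyses may be needed"; any that are added are to be documented in the study report.
- **Per-protocol set (SAP 5.4).** Major violations include an undefined residual category, and this set is used for sensitivity analyses of both primaries.

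**The concern.** An interim for the sponsor's own planning differs from one held behind a monitoring committee, because the recipient also runs the trial, cleans the data and finalises the analysis. If results by arm reach people with those duties before lock, three things can follow the result: which data are queried, which violations count as major, and how the discretionary model terms are settled.

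This matters most for SpO2/FiO2, because its endpoint is Day 10 or discharge and the look is in effect its final analysis. SAP section 2 declares success if either primary is significant, with no multiplicity adjustment, so latitude in one model can decide the trial.

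**Working it through.** **Plan's own figures.** For time to recovery, with allocation 1/3 to 2/3 and effect log(0.5), the required events are (1.960 + 0.842)² / [(1/3)(2/3)(0.693)²] = 73.5. With 75 events the power is 0.808, so the stated 80% reproduces. (SAP section 3 prints the inverse of the log hazard ratio; taken literally that gives about 17 events.) For SpO2/FiO2, (1.960 + 1.282)² / [(2/9)(0.625)²] = 121, and 80 against 40 gives power 0.898, or 0.893 with the t distribution. The design figures stand; this point concerns conduct.

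**SpO2/FiO2.** The trigger is the last patient's Day 10 and the endpoint is Day 10 or discharge. All participants have therefore reached the endpoint, and the information fraction is about 1.0.

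**Time to recovery.** Inputs from the documents: 120 planned participants (80 active, 40 placebo), follow-up to Day 28, placebo median 12 to 15 days, and about half completed when enrolment closed. Assumptions: the planned number was enrolled; accrual was uniform with half enrolled in the last 28 days, hence 56 days in all; the interim is held at its earliest date; recovery times are exponential; and the recovery rate ratio is 1 (no effect) or 2 (the plan's halving of time).

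Patients short of Day 28 are those enrolled in the last 18 days: 18/56 = 32%, about 39 of 120. With median m and λ = ln 2 / m, the expected events still to come, per enrolled patient, are

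(1/56) × { [2^(−10/m) − 2^(−28/m)] / λ − 18 × 2^(−28/m) }.

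For m = 12 this is (1/56) × (6.28 − 3.57) = 0.0484.

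| Placebo median | Rate ratio | Outstanding per patient, placebo / active | Outstanding of 120 | Events by Day 28 | Share outstanding |
|---|---|---|---|---|---|
| 12 | 1 | 0.0484 / 0.0484 | 5.8 | 96.2 | 6.0% |
| 15 | 1 | 0.0493 / 0.0493 | 5.9 | 87.1 | 6.8% |
| 12 | 2 | 0.0484 / 0.0299 | 4.3 | 108.9 | 4.0% |
| 15 | 2 | 0.0493 / 0.0380 | 5.0 | 103.0 | 4.9% |

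So about 4 to 6 recoveries are outstanding. The exponential curves give more events than the 75 the plan counts on; 4.0% to 6.8% of 75 is 3 to 5, which leads to the same conclusion. The patients still under follow-up without an event number about 8 to 17, of whom these 4 to 6 are expected to recover by Day 28.

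**What model choice could cost (illustration only).** Suppose the most favourable of 2 to 4 candidate models were chosen after seeing results, with test statistics correlated 0.80 to 0.95. By simulation, the one-sided error per endpoint rises from 0.025 to between 0.032 (two models, correlation 0.95) and 0.058 (four models, correlation 0.80). The correlations are assumed, and nothing in the plan instructs anyone to choose this way.

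**The case against.** **Results by arm are not expressly promised to the sponsor.** Section 5.10 gives only a purpose. The endpoint list follows the restated committee plan, so its application to this look is an inference. This stands, and it is why the point is framed as a gap in what the SAP states.

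**Much of the model is rule-based.** The stepwise threshold, the 5% removal rule and the AIC fallback for covariance are written in advance. Days 6 to 9 depend on discharge timing, which can be judged without treatment codes, and the reported contrast stays at Day 10/discharge. The extra sensitivity analyses are not the primary model, and neither primary has an optional transformation. This also stands, but it leaves the permissive wording for added covariates, time points and sensitivity analyses. The p-value rules also depend on data that can still be queried.

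**The SAP has a safeguard.** Its Introduction routes changes to the primary analyses through a protocol amendment and requires deviations to be justified in the study report. That governs departures from the plan; it does not close discretion already written into it.

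**The setting limits the harm.** Enrolment was complete, dosing ends by Day 10 or discharge, Phase 3 is to be analysed separately, and no text releases results to sites. The look spends no alpha if it cannot stop the trial. All of this stands and lowers the weight of the point.

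A reader might also infer that 28% to 36% of primary events are still to come, because 2^(−10/m) − 2^(−28/m) is 0.363 and 0.356 for placebo medians 12 and 15, and 0.276 and 0.322 for active medians 6 and 7.5. That is the chance that one patient's event falls between that patient's own Day 10 and Day 28. It would be the outstanding share of patients only if everyone were at Day 10 at the look. Likewise, the half of patients not yet complete belongs to the earlier committee look.

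**Conclusion.** The concern holds in a limited form. The SAP plans a sponsor interim before lock and states neither recipients, content by arm and firewall, nor a freeze of the primary models. The exposure is greatest for SpO2/FiO2, which is complete at that point. For time to recovery, about 4 to 6 of 120 events (roughly 4% to 7%) are outstanding, under the accrual and exponential assumptions above and the earliest interim date; a later date leaves fewer.

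The main route to bias is therefore data queries, exclusions and model choice. Bedside assessment is a minor one, since summaries by arm do not disclose individual assignments. The documents do not support saying that the Phase 2 result is already compromised or that the sponsor will certainly see efficacy by arm. The regulator's lack of objection, as section 5.10 reports it, concerned the Phase 3 approach and does not settle the Phase 2 models. The improvement is cheap and worth making.

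**What to change.** Before any release by arm:

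1. Amend the SAP to fix the covariates for both primaries and the MMRM time points. One option for the covariates is the set in protocol section 9.4.2, with corticosteroid use either in or out by decision. Whether to include Days 6 to 9 can be settled from pooled discharge times.
2. List the sensitivity analyses, and settle major violations on blinded data.
3. Have the existing separate unblinded team produce the interim. State its content, and release it only to named Phase 3 planners.
4. Keep sites, data management and the final-analysis statisticians blinded until the Day 28 lock.

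Cost: SAP text, with a protocol amendment where the SAP's own rule on primary analyses requires one; a recipient list; a data cut before the look; and fewer sponsor staff seeing early results. The data cut takes some work, so an effect on the planning timetable cannot be ruled out from the documents.
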